### 10.2 Unblinding

Unblinding will take place after locking of the final database. It will be performed in SAS® by combining the imported randomisation list and each SAS® table containing relevant information for the trial. Randomisation numbers are used to match files correctly. The corresponding code will be filed.

Blinded and unblinded data will be listed separately.

### 10.3 Treatment of baseline values

Within the study, change from baseline in IELT with the 5% Benzocaine condom versus the standard NRL condom, over a 4-week assessment period.

### 10.4 Categorisations

As part of the analysis, three categorisations of the subjects are carried out.

1. Proportion of subjects who achieve an increase of 2 mins from baseline in IELT in the 5% benzocaine condoms compared to the standard NRL condom are placed in category 1. Those subjects who do not meet this condition are placed in category 0.
2. Proportion of subjects who achieve an increase of 3 mins from baseline in IELT in the 5% benzocaine condoms compared to the standard NRL condom will receive a category 1. Those subjects who do not meet this condition are placed in category 0.
3. Proportion of subjects who achieve an increase of 4 mins from baseline in IELT in the 5% benzocaine condoms compared to the standard NRL condom are placed in category 1. Those subjects who do not meet this condition are placed in category 0.
4. Proportion of subjects who achieve an increase of 2 mins from baseline in IELT in the 3% benzocaine condoms compared to the standard NRL condom are placed in category 1. Those subjects who do not meet this condition are placed in category 0.
5. Proportion of subjects who achieve an increase of 3 mins from baseline in IELT in the 3% benzocaine condoms compared to the standard NRL condom will receive a category 1. Those subjects who do not meet this condition are placed in category 0.
6. Proportion of subjects who achieve an increase of 4 mins from baseline in IELT in the 3% benzocaine condoms compared to the standard NRL condom are placed in category 1. Those subjects who do not meet this condition are placed in category 0.

### 10.5 Calculation of derived variables

#### Difference to baseline

Difference to baseline values will be calculated per subject and assessment time as:

$$Diff\_Variable_{t_{ij}} = Variable_{t_{ij}} - Variable_{t_{0j}}$$

for  $t_0 = \text{Baseline}$   
 $t_i = \text{assessment time after application, } i \in \{1, \dots, k\}$   
 $j = \text{subject number } j = 1, \dots, n$

Differences from baseline are calculated for the following variables:

- Intravaginal Ejaculation Latency Time (IELT) with Test Condom A, B and Standard NRL condom

### **Overall proportion of subjects with adverse events / adverse device effects**

Proportion of subjects with an (S) AE or S (ADE).

$$Proportion \pi = \frac{n_{AE}}{N} \cdot 100$$

for  $n_{AE} = \text{number of subjects with at least one (S)AE or (S)AD}$   
 $N = \text{total number of all subjects}$

Note: The proportions are given in percent.

### **Overall proportion of clinical failure event**

$$Proportion \pi = \frac{n_{CF}}{N} \cdot 100$$

for  $n_{CF} = \text{absolute number of clinical breakage or clinical slippage of condom (defined by ISO 29943-1)}$   
 $N = \text{total number condom usage}$

Note: The proportions are given in percent.

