## 8 Analysis Datasets

The analysis populations will be as follows:

- The safety population will include all randomised subjects who use at least one of the study condoms. The safety population will be used for all baseline summaries and summary of safety data. For the safety population, subjects will be analysed according to treatment received.
- The Full Analysis Set (FAS) will include all randomised subjects who use at least one of the study condoms and who have IELT recorded in at least one of the post-baseline study periods. The FAS will be used for the analysis of all efficacy endpoints. For the FAS, subjects will be analysed according to their randomised treatment.
- The Per Protocol (PP) population will consist of all subjects in the FAS who do not deviate from the protocol in such a way as to impact the evaluation of the primary endpoint. Subjects who do not have an IELT recorded for at least 4 condom uses within a treatment period will be excluded from the PP population for that period. All decisions on exclusions from the PP population will be made prior to database lock. For the PP population, subjects will be analysed according to treatment received.

The final assignment to the FAS and PP population is based on the data review meeting prior to database hardlock. The data review meeting committee is composed of different experts from the sponsor and the CRO.

The disposition of all subjects is shown using a flow chart including all screened subjects.

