##### Other variables

- Start date and time of intercourse [dd.mm.yyyy – hh:mm] + [single choice check box]
  - Date and time
  - The intercourse did not proceed
    - Specification why not proceed
- Report of condom breakage and condom slippage during the vaginal intercourse or withdrawal from the vagina.[multiple choice check box]
  - Condom broke
  - Condom completely slipped off from the base of the penis during intercourse
  - Condom completely slipped off from the base of the penis during withdrawal from the vagina
    - Hold on to the base of the condom during withdrawal from the vagina [yes/no]
  - No condom breakage or complete condom slippage
- Reaction to condom breakage or complete condom slippage [single choice check box]
  - Removed condom and carried on without a condom
  - Did not proceed further with intercourse.
  - Not applicable since the condom did not break or completely slip
- Usage of lubricant [single choice check box]
  - Yes, the investigation lubricant was used
  - Yes, another type of lubricant was used
    - Specification of other

- No
- Date and time of completing this IELT diary [dd.mm.yyyy – hh:mm]

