**For primary endpoint:**

The primary endpoint of the investigation is the change from baseline in IELT with the 5% Benzocaine condom versus the standard NRL condom, over a 4-week assessment period. For each subject, a mean IELT will be calculated across all intercourse episodes within a study period (baseline, assessment period 1, assessment period 2 and assessment period 3) and used for analysis.

For the calculation of the respective mean values, only IELT data points that were generated during a condom-based clinical-failure-free sexual intercourse are taken into account. Ejaculation is to be considered the posterior threshold.

If an IELT value is not considered valid due to the regulation listed in table 19.6 located in the appendix, it is not used in the calculation and is formally considered non-existent in the primary and secondary analyses. This value is also not considered further in any descriptive analysis.

Consequently, the classification of some values as "non-valid" can affect the categorization of the FAS and PP analysis population, as excluded IELT values cannot be evaluated in this consideration either.

The change from baseline in IELT will be analysed using a linear mixed model using data from all three condom groups, with the primary comparison between the 5% benzocaine condom with the standard NRL condom. The model will include fixed effects for treatment and period, a covariate for baseline IELT, and a subject as a random effect. The differences between the 5% benzocaine condom and the standard NRL condom will be presented with a 95% CI and an associated p-value. Statistical significance will be assessed at the two-sided 5% level. No adjustment for multiplicity will be made since there is a single primary comparison (5% benzocaine condom versus standard NRL condom). No assumptions of normality will be checked based on utilizing the Generalized Linear Mixed Model (GLMM) to analyze the primary endpoint. If the model can't handle the violation, a non-parametric model will be used in the worst-case scenario, such as Wilcoxon signed ranks test with Hodges Lehmann estimator for treatment differences.

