- The PGIC recorded at the end of each condom assessment period will be summarised by condom type, as the number and percentage in each category of the PGIC (Very much better, Better, Little better, No change, Little worse, Worse, Very much worse). A comparison of the PGIC in each of the 5% and 3% Benzocaine condoms versus the standard NRL condom will be performed using a GLMM, assuming a multinomial distribution for the response variable. Factors in the model will include fixed effects for treatment and period. Subject will be included as a random effect. Comparison between the 5% and 3% Benzocaine condoms with the standard NRL condom will be expressed as an odds ratio, with an associated 95% CI and p-value. In the event that some categories of the PGIC have too few subjects for the model to fit, the number of categories in the PGIC responses may be reduced (e.g., better, no change, worse) for purposes of analysis.

A measure of EMSEX pleasure scale at the end of each 4-week assessment period, in subjects using the 5% and 3% benzocaine condoms compared to the standard NRL Condom.

- After each coital act, the mean of the responses on the EMSEX pleasure scale (0 to 100) will be calculated as the sum of responses divided by number of questions answered. For each condom assessment period, a subject-level mean EMSEX pleasure scale will then be derived using data from all coital acts. The EMSEX pleasure scale score will be analysed using a linear mixed model using data from all three condom groups, with comparisons between the 5% and 3% Benzocaine condoms with the standard NRL condom. The model will include fixed effects for treatment and period, and subject as a random effect. The between group differences will be presented with a 95% CI and an associated p-value.

User acceptability, experience and preference of each condom type will be evaluated through subject perceived questions, asked at the end of each 4-week assessment period.

- Responses to SPQs will be summarised for each condom type using descriptive statistics.

The in-use tolerability of each condom type will be evaluated through subject perceived questions, asked at the end of each 4-week assessment period.

A measure of the total clinical failure rate (in percent) of Test Condom A, Test Condom B and Control NRL condom, where as a failure is defined if at least one of the following variables are met (specified according to the high level definition of ISO-29943-1):

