## Overview

The summary of the statistical analysis scheme is presented in the following table:

Target variables	Population	Graphs	Statistical methods
Disposition of subjects	SP	Flowchart	
Disposition of investigational products	SP	Flowchart	
Baseline characteristics	SP		
childbearing potential, ethnicity, physical examination	SP	--	Counts and percentages
Age, height, weight, BMI	SP	--	Descriptive statistics
Medical history	SP	--	Counts and percentages
Primary variable*	FAS*, PP**		
IELT with the 5% Benzocaine condom A		Bar chart	Descriptive statistics 95 % Confidence Intervals GLMM or Wilcoxon signed ranks test
Secondary variable(s)	FAS		
IELT with the 3% Benzocaine condom B	FAS**, PP**	Bar chart	Descriptive statistics 95 % Confidence Intervals GLMM or Wilcoxon signed ranks test
EMSEX Pleasure Scale for Test Condom A OR B against standard NRL condom	FAS**	--	Descriptive statistics 95 % Confidence Intervals GLMM or Wilcoxon signed ranks test
Patient Global Impression of Change (PGIC)	FAS**	--	Counts and percentages GLMM or Wilcoxon signed ranks test 95 % Confidence Intervals
Subject perceived questions	FAS**		Counts and percentages

Target variables	Population	Graphs	Statistical methods
Proportion of subjects who achieve an increase of 2 mins from baseline in IELT	FAS**, PP***	--	Descriptive statistics Counts and percentages GLMM or Wilcoxon signed ranks test 95 % Confidence Intervals
Proportion of subjects who achieve an increase of 3 mins from baseline in IELT	FAS**, PP***	--	
Proportion of subjects who achieve an increase of 4 mins from baseline in IELT	FAS**, PP***	--	
Total clinical failure rate	FAS**	--	Descriptive statistics Counts and percentages

\*: Confirmatory hypothesis testing

\*\*: No confirmatory hypothesis testing, part of secondary analysis

\*\*\*: Provided that the rule for sensitivity analysis from chapter 12.2 applies.

Additional tables and figures are acceptable for illustrative purposes. Additional statistical tests can be performed, if reasons are given in the final report. The corresponding p-values have to be interpreted purely descriptive in the context of an explorative data analysis.

Examples of crucial tables, listings and figures can be seen in Chapter 19.

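### The condom failure rate is computed in the FAS, whose membership after Amendment 1 can depend on condom failure, so the rate can be biased low; the safety population avoids this

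*SAP*

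**What the plan says.** Slippage and breakage performance is a secondary objective of its own (Protocol 2.1, SAP 4). Its endpoint is the total clinical failure rate.

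- **Formula.** SAP 10.5 takes as numerator the "absolute number of clinical breakage or clinical slippage of condom" and as denominator the "total number condom usage".
- **Definition of a failure.** SAP 11.4 (secondary endpoints) says that "a failure is defined if at least one of the following variables are met". Table 19.6 gives a single yes/no for clinical failure per record.
- **Analysis set.** The SAP Overview table lists "Total clinical failure rate" under the FAS. Table 14.2.2.25 stands under a heading that also names the FAS.
- **FAS and safety population.** SAP 8 limits the FAS to randomised condom users "who have IELT recorded in at least one of the post-baseline study periods" and analyses them by randomised treatment. The safety population takes every randomised subject who used at least one study condom, without an IELT condition, by treatment received.
- **Amendment 1.** SAP 11.4 (primary endpoint) treats a non-valid IELT as non-existent and states that this "can affect the categorization of the FAS and PP analysis population". Under Table 19.6, an IELT is non-valid if the condom broke or slipped off completely during intercourse. Slippage at withdrawal without breakage leaves the IELT valid.

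**The concern.** Taken together, these rules let the outcome decide who is analysed. If every condom a couple used broke or slipped off during intercourse, the couple has no valid IELT. It is then not in the FAS, and its failures are missing from the device-failure rate. Such couples are the ones with the worst experience of the product.

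The route is a realistic one. The diary lets a user stop intercourse after a failure (SAP 9.1), and Protocol 4.5 includes inadequate device performance among the grounds for withdrawal. At stake is a device-performance rate that could look slightly better than it was, by an amount the report would not show.

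**Working it through.** **Inputs from the documents.** 135 to complete, 150 randomised, 10% dropout (Protocol 3.3); at least 4 IELT records per period (Protocol 7.3); 8 condoms supplied per type (Protocol 3.1). The documents state no expected failure rate, so there is no plan figure for this endpoint to reproduce. The size figures can be checked. The SD of the paired difference is 7.1 × √(2 × (1 − 0.5)) = 7.1 min. A two-sided 5% paired t-test for 2 min at 90% power then needs 135 (exact power 0.901; the normal approximation gives 133), and 135 / 0.90 = 150. That leaves 15 expected dropouts.

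**Assumptions.** The per-use failure rate p is 2%, with a range to 10%. Every failure is of a kind that invalidates the IELT; withdrawal slippage would lose less. The 15 dropouts split evenly, 5 per condom type. Completers use 4 or 8 condoms per type.

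**Step 1: completers.** A completer has at least 3 × 4 = 12 uses and leaves only if all 12 fail. With independent uses the chance is 0.02¹² ≈ 4 × 10⁻²¹, and at 10% it is 10⁻¹². With strong clustering (beta-binomial, intraclass correlation 0.3) it is about 0.02% at p = 2% and 0.05% at p = 5%, or 135 × 0.0005 ≈ 0.07 couples at most. The issue therefore concerns early dropouts.

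**Step 2: dropout unrelated to failure.** Each dropout uses one condom. Per type, U = 135 × m + 5 condoms (m = uses per completer), F = p × U failures, and r = 5 × p failed condoms removed with their couples. The safety rate is F/U and the FAS rate is (F − r)/(U − r).

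| p | m | U | F | r | Safety | FAS | Difference (points) |
|---|---|---|---|---|---|---|---|
| 2% | 4 | 545 | 10.9 | 0.10 | 2.000% | 1.982% | 0.018 |
| 2% | 8 | 1,085 | 21.7 | 0.10 | 2.000% | 1.991% | 0.009 |
| 5% | 4 | 545 | 27.25 | 0.25 | 5.000% | 4.956% | 0.044 |
| 10% | 4 | 545 | 54.5 | 0.50 | 10.000% | 9.917% | 0.083 |
| 10% | 8 | 1,085 | 108.5 | 0.50 | 10.000% | 9.959% | 0.041 |

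**Step 3: dropout caused by failure.** Let k couples in one type each quit after a single failed condom. Completers have U = 135 × m and F = p × U. The safety rate is (F + k)/(U + k) and the FAS rate is F/U. At p = 2%:

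- k = 1, m = 4: (10.8 + 1)/(540 + 1) = 2.181% against 2.000%, a loss of 0.18 points.
- k = 1, m = 8: (21.6 + 1)/(1,080 + 1) = 2.091% against 2.000%, a loss of 0.09 points.
- k = 5 (all 15 dropouts, 5 per type): 15.8/545 = 2.90% for m = 4 and 26.6/1,085 = 2.45% for m = 8, against 2.00%.

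The loss per couple hardly depends on p: for k = 1 it is 0.183 (m = 4) or 0.092 (m = 8) points at 1%, and 0.166 or 0.083 at 10%.

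**The case against.** The exclusion is narrow. One valid IELT in any of the three periods keeps the couple in the FAS with all its failures, and Amendment 1 deletes the IELT value, not the failure record. The endpoint is descriptive, the SAP lists all collected data (19.5), and device deficiencies are tabulated in the safety population. No passage says that failures cause dropout. If they do not, 15 dropouts with one condom each give 15 × 0.02 = 0.3 affected couples in the whole trial. All of this stands, and it limits the point to a minor one.

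Two stronger readings are tempting, and the documents support neither.

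- A reader might infer that the formula in 10.5 counts a condom twice if it both slipped and broke, because the diary item allows several ticks. An event count would show 2.1% or 2.5% for a true 2% if 5% or 25% of failed condoms had two ticks (2% × 1.05, 2% × 1.25). But SAP 11.4 defines a failure as at least one mode being met, and Table 19.6 gives one yes/no per record even where several modes are present. Under that definition the excess is zero; 10.5 is loosely worded, no more.
- A reader might infer that requiring a valid IELT can only remove failures. That holds for the Amendment 1 exclusion. The diary also has IELTs missing because of the stopwatch or because there was no ejaculation (SAP 9.1). A couple with only such records takes failure-free condoms out of the denominator, which raises the rate.

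**Conclusion.** The point holds as a minor weakness. After Amendment 1, the failure rate is computed on a set whose membership can depend on failure, and through this route the rate can be biased low. That the reported rate will in fact be biased is not shown. With the assumptions above, the loss per type is negligible if dropout is unrelated to failure. It reaches 0.45 to 0.90 points at a 2% rate only if all 15 expected dropouts quit because their single condom failed. The failure rate, the timing of dropout and its link to failure are all assumed. The randomised-versus-received rule is a further, unquantified reason to leave the FAS for this endpoint; it matters only if a wrong condom type is used.

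**What to change.** In the SAP Overview table, 10.5 and Table 14.2.2.25, compute the total clinical failure rate on the safety population by condom type received. Use all condoms used as the denominator, whether or not the IELT is valid. Reword the numerator in 10.5 as the number of condoms with at least one clinical failure, to match 11.4 and Table 19.6; this is a clarification, not the correction of a demonstrated bias.

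One separate item needs settling in the same edit. Item 3 of the failure list in 11.4 counts slippage at withdrawal because the user did not hold the condom as a failure. Table 19.6 and its note 4 call the same event non-clinical, and where it is the only event they set clinical failure to No. These passages must be reconciled, since 10.5 cannot agree with both.

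The cost is a few lines of SAP text and the matching table programming. The safety population is already defined and the diary already holds the data. The change should be made before database lock, with a note in SAP 15 if the sponsor regards it as a departure from Protocol 9.3.

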## **10.6 Treatment of missing values**

In case of the occurrence of missing data, the following rules apply:

### **IELT**

There will be no imputation for missing data. By using a mixed model, subjects who provide data for only one or two of the three assessment periods will be included in the FAS-analysis. For the calculation of mean IELT within an assessment period, only intercourse episodes where IELT is recorded will be included in the analysis.

### **EMSEX**

For the calculation of the mean EMSEX pleasure score (using the 11-items), if more than 5 of the 11 items are missing for a particular coital act, the EMSEX pleasure score will be set to missing for that coital act.

If less equal 5 items are missing, the EMSEX pleasure score is calculated as the mean of the available (answered) item.

No imputation of missing values will be performed.

PGIC

Subjects with a missing PGIC score will be omitted from the respected PGIC analysis.

Subject Perceived Questionnaire

No imputation of missing values will be performed.

Global evaluation of effectiveness, tolerance, and usability

No imputation of missing values will be performed.

**10.7 Treatment of outliers**

No replacement of outlying data values will be performed.

## 11 Statistical methods

### 11.1 Dichotomous and categorical variables

For all dichotomous and categorical variables, absolute and relative frequencies will be calculated if not stated otherwise.

For safety variables – separated by subject and partner:

Two separate counting rules apply for AEs:

- Total number of AEs (possibly counting subjects with several AEs more than once)
- Total and relative number of subjects suffering from at least one AE
- The overall proportion of AE subjects with last safety objective

Frequencies of AEs will be summarized in tables overall, by system organ class (SOC) and preferred term (PT) based on MedDRA Coding (Version 26.1 or higher) including only TE AEs and TE ADEs, which will be summarized (incidence and frequency) separately for males and females, by treatment group.

Two separate counting rules apply for changes in prior and concomitant therapies:

- Total number of changes in concomitant therapies (possibly counting subjects more than once)
- Total and relative number of subjects receiving at least one change in concomitant therapies.

Two separate counting rules apply for concomitant diagnoses:

- Total number of diagnoses/therapies (possibly counting subjects more than once)
- Total and relative number of subjects having at least one diagnosis/therapies. ,

### 11.2 Continuous and quasi-continuous variables

For all continuous and quasi-continuous variables, the following sample characteristics will be calculated for descriptive presentation:

- count of subjects evaluated (n)
- arithmetic mean (Mean)
- standard deviation (SD)
- median (Median)
- minimum (Min)
- maximum (Max)
- lower confidence interval limit (lower CI limit)
- upper confidence interval limit (upper CI limit).
- 

